5.4.3 UNBLINDING PROCEDURES

There are no current plans to systematically unblind participants to the treatment they may or may not have received during the clinical trial. However, following the completion of data collection, participants may contact the [name] Lab for unblinding information.

6 STUDY PROCEDURES/EVALUATIONS

6.1 SELF-REPORT MEASURES

During the telephone screening, researchers will collect demographics, which include medical history and medication history. In addition, several other self-report measures will be used throughout this study. These measures are listed below and can be found in the attached documents.

- A. THE PERCEIVED STRESS SCALE (PSS) is a 10-item self-report assessment using a 5-level Likert scale to assess the degree to which an individual perceives life events as stressful in the past month. This scale is the most commonly used measure of self-reported stress, and produces results that are valid for 4-8 weeks after administration (Cohen & Williamson, 1988).
- B. THE STATE-TRAIT ANXIETY INVENTORY (STAI) is a 20-item self-report assessment that assesses either temporary or chronic anxiety. For the purposes of this study, the state version will be used to measure anxiety as a result of the stress condition. The STAI is commonly used to assess both types of anxiety, and has applications in both clinical and research settings (Spielberger et al, 1983).
- C. THE BEHAVIORAL INHIBITION AND BEHAVIORAL APPROACH SYSTEM SCALES (BIS/BAS) are a set of 24 questions used to assess an individual's sensitivity to approach vs. inhibition in motivating behavior. This scale is commonly used to measure behavior and has been demonstrated to be reliable (Carver & White, 1994).
- D. THE CONNOR-DAVIDSON RESILIENCE SCALE (CD-RISC) is a 25-item self-report assessment using a 5-level Likert scale to assess the degree of resilience an individual displays to stressful events. This scale has been shown to be a reliable measure of resilience, correlating with improvement during treatments designed to improve anxiety disorders (Connor & Davidson, 2003).
- E. THE POSITIVE AND NEGATIVE AFFECT SCHEDULE (PANAS) is a 20-item self-report assessment using a 5-level Likert scale to assess the positive and negative affect of an individual over the past week. This scale has been shown to be a reliable measure of both positive and negative affect with little subjectivity to demographic variables (Watson et al, 1988).

6.2 SPECIAL ASSAYS OR PROCEDURES

Each participant will receive two days of stimulation, separated by a week. One session will involve 10Hz tACS, and the other will involve active sham; the order of stimulation condition will be randomized for each participant. For more information on the stimulation procedures, see section 7.2 *Preparation and Administration of Study Investigational Product*.

6.3 SAFETY MEASURES

We will be monitoring the safety of our participants throughout the study with the following measures. These measures are listed below and can be found in the attached documents.

- A. A stimulation adverse effects questionnaire used in previous studies (IRB #14-1622, #14-3285, and #14-0600) will be administered at the end of each stimulation session. This questionnaire will be used as a safety measure and to collect data on participant experience. Please see 10.1 *Safety Parameters* for more information.

6.4 LABORATORY EVALUATIONS

6.4.1 SCREENING LABORATORY EVALUATIONS

A urine pregnancy test will be performed for any female participant who is unable to confirm pregnancy status. All participants will also undergo a urine drug test.

INSTRUCTIONS FOR SPECIMEN PREPARATION, HANDLING, AND STORAGE. For this laboratory evaluation, results are available after only a few minutes. Once the results are clear, the researcher will make a note and the sample will be disposed. All samples will be handled using single-use disposable medical gloves.

6.4.2 SALIVA SAMPLES

We will be collecting a saliva sample at the first session. This sample will be used to test for a single nucleotide polymorphism in the BDNF gene whose presence may have an influence on effectiveness of brain stimulation. Within the central nervous system, BDNF regulates survival, proliferation, and synaptic growth as well as directly influences synaptic plasticity in the adult human brain (Antal et al., 2010). Egan et al. (2003) demonstrated that Val66Met, a single nucleotide in the BDNF gene, has function consequences in healthy humans, including decreased episodic memory and hippocampal inducing a reduction in recall capacity. This polymorphism is common in over one third of the Caucasian population (65% Val66Val to 35% Val66MET) (Pezawas et al, 2004; Hariri and Weinberger, 2003). Kleim et al. (2006) found that individuals with the Val/Val polymorphism respond to tDCS and transcranial magnetic stimulation (TMS) treatments with expected change, whereas, individuals expressing Val/MET allele do not. These authors indicate the difference to be caused by the impairment in synaptic plasticity caused by the Val/MET allele. These findings suggest that individual efficacy of treatments using brain stimulation may be partially genetically predetermined and should be taken into account when performing such procedures. Accordingly, we will conduct genotyping of all participants in this study in order to assess BDNF status. We will perform exploratory analyses in which we group participants by BDNF status.

We will also be collecting two saliva samples at each session to test for a cytokine panel, salivary alpha-amylase, and cortisol as measures of immunity and stress.

INSTRUCTIONS FOR SPECIMEN PREPARATION, HANDLING, AND STORAGE. The saliva samples for BDNF testing will be collected using 2mL DNA collection kit from DNA Genotek. Before sample collection, it is imperative that the participant does not eat, drink, smoke or chew gum for at least 30 minutes before providing a sample. Once the participant provides the 2mL sample, the collection tube is closed and a liquid from the lid will be released into the tube. The original lid will be removed and replaced with a small cap and the tube will be agitated for 5 seconds. The sample is then returned to the plastic packaging and labeled with the date of collection, the study name, and the participant ID. These samples are kept in a secure location until the completion of data collection.

Saliva samples at each session will be collected using the Passive Drool collection kit from Salimetrics. These samples will be labeled with the study name and participant ID, and frozen immediately after collection until completion of all data collection.

7 STUDY INVESTIGATIONAL PRODUCT

7.1 DEVICE DESCRIPTION

We will be using the XCSITE100 stimulator designed in the [name] Lab for investigational purposes. The device is not implanted and has not been designed for or being used to support or sustain human life. This device does not have a potential for serious risk to the health, safety, or welfare of the participant. There has never been an instance of serious side-effect reported due to the use of transcranial brain stimulation. Previous studies in the [name] lab that used comparable devices (i.e., the commercial, CE-certified Neuroconn Plus stimulator) have always been classified as “non-significant risk” by the full UNC IRB. The Neuroconn Plus stimulator and the XCSITE100 stimulator are electrically equivalent and provide the same stimulation.

The XSCITE100 is the first non-invasive brain stimulator designed for research purposes to provide an active sham for tACS and record the stimulation output for later validation. This stimulator may apply either tDCS or tACS for up to 40 minutes (2400 seconds) with appropriate current ramp-up at the beginning of stimulation and ramp-down at the end of stimulation. Both tDCS and tACS may be applied for currents between 100 μ A and 2 mA (peak-to-peak for tACS).

The stimulator has two main components:

1. Android tablet with user interface application (i.e., App)
2. Stimulator with:
 - a. Microprocessor
 - b. Function generator chip
 - c. Voltage controlled current source
 - d. Safety circuitry

To ensure appropriate blinding for each stimulation session, there are designated unblinded individuals to ensure the appropriate stimulation parameters are applied to each participant. These individuals will not interact with participants and will only be involved with the creation of a study file and validation of stimulation waveform.

7.2 SAFETY FEATURES

Current Sensor Circuit. A 33.2 Ω sense resistor is placed in series with the stimulation electrodes on the high side. Since high-side current sensing is used, any short circuit of the electrode terminals to ground will be detected. The stimulation current flows through this resistor and creates a voltage. The voltage across this resistor is sensed and amplified by the AD628 difference amplifier. The gain of the difference amplifier is set to 9.9039. The current sensor voltage is then shifted before it is read by the microprocessor and the hardware current safety feature.

Voltage Sensor Circuit. The differential voltage across the electrodes is measured so that the impedance can be calculated. The voltage is measured by buffering the positive electrode and negative electrode each with a unity gain op-amp circuit. The voltage output is then shifted before it is read by the microprocessor using the same level shifting circuit described in the current sensor section.

The device is equipped with 4 different stages of safety precautions, all of which protect the participant from high currents. The stages are as follows:

[figure not shown]
1. AUTOMATIC SOFTWARE CURRENT CUTOFF. The output of the current sensor described above is read by a microprocessor, which compares the reading to a value of ± 3 mA peak. If the current exceeds these limits,

CONFIDENTIAL

stimulation is stopped, a relay in series with the electrode is opened, and the power supply used for stimulation is turned off. The user is then given the option to investigate the issue, and cancel or resume the test. Since high-side current sensing is used (described above), any short circuit of the electrode terminals to ground will be detected.

2. **AUTOMATIC HARDWARE CURRENT CUTOFF.** The output of the current sensor is fed into a pair of comparators which detect if the current exceeds ± 4.5 mA. If so, the fault is latched such that the relay in series with the electrodes is opened. Additionally, the microprocessor is notified of this instance through an interrupt. Upon this interrupt, the microprocessor immediately stops stimulation and the power supply used for stimulation is turned off.

Figure 1. Example of a successful hardware cutoff function

3. **PERMANENT HARDWARE CURRENT CUTOFF.** A 5 mA fast-acting fuse is in series with the electrode connector. If the above two over-current detection methods fail, the fuse will blow, and the stimulator will no longer be electronically connected to the device.
4. **POWER SUPPLY FUSE.** Finally, if for no other reason the entire device draws too much current, the main power supply fuse is blown. This fuse is sized with a cutoff of 200% of steady-state operating current.

7.3 PREPARATION AND ADMINISTRATION OF STUDY INVESTIGATIONAL PRODUCT

After participants have completed the questionnaires, they will be comfortably seated. The research team will first measure their heads electrode placement using the 10-20 system. Participants will then be fitted with the 3 electrodes for stimulation. The participant will be in the relaxed yet, experimentally controlled state by watching a nature movie. One session of stimulation will be performed per visit for 40 minutes. During the 10 Hz tACS

condition, participants will have a 10 second ramp in and ramp out with 40 minutes of stimulation for a total of 2420 seconds. Stimulation waveforms are sine-waves with a peak-to-peak amplitude of 2 mA. The sham stimulation will include 10 seconds of ramp in to 1 minute of 10 Hz tACS with a ramp out of 10 seconds for a total of 100 seconds of stimulation. Electrodes will be saline soaked, 5x5cm and placed over F3 and F4 with a 5x7cm placed over CZ as a return electrode.

Stimulation devices will be preprogrammed and codes will be randomized to one of the two experimental arms. Researchers will enter the participant-specific code into the App that controls the stimulation and monitor participants during the 40 minutes of the stimulation.

The study coordinator and/or the research assistant will be thoroughly trained and have trainings documented on the transcranial stimulation device and will be present during all stimulation sessions. *Please see Appendix F for an example of the training documentation log.* To monitor side effects of stimulation a questionnaire will be administered after each stimulation session. *Please see Attachment 1 for an example of the stimulation questionnaire.*

7.4 ASSESSMENT OF PARTICIPANT COMPLIANCE WITH STUDY INVESTIGATIONAL PRODUCT

Compliance for this study includes attending both sessions. Individuals who miss a session and are unable to reschedule within one week will be dropped from the study.

8 POTENTIAL RISKS AND BENEFITS

8.1 BENEFITS TO SUBJECTS AND SOCIETY

The results of this study have major implications for the use of tACS as a treatment method for alleviating stress and symptoms of stress. One such symptom is compromised immune functioning, which has been demonstrated as detrimental especially in students and other individuals experiencing high levels of acute stress. The results of this study may also prompt further investigation into the relationship between cortical oscillations and immune functioning.

This study is not designed to benefit the individual participants. However, participants may experience some acute or even chronic stress relief as a result of the treatment. There are no serious risks to the participant from the treatment used in this study.

8.2 POTENTIAL RISKS

8.2.1 PSYCHOLOGICAL

Emotional Distress: As part of data collection, participants will undergo a timed mental arithmetic task designed to induce psychological stress. This task is meant to induce a short-term stress response via enhanced secretion of catecholamines. Such a response occurs naturally in the body and has not shown any long-term negative side effects. In order to protect the integrity of results, participants will not be made aware of the purpose of the task until after completion of the final session.

8.2.2 PHYSICAL

Risk of Injury and Discomfort: Transcranial current stimulation has been used without any reports of serious side-effects for more than a decade. This stimulation made has NOTHING to do with electroconvulsive therapy that applies many orders of magnitude higher stimulation current. Rather, transcranial current stimulation is so weak that it does not cause super-threshold activation of neurons ([name] and McCormick, 2010). In particular, tACS has been used without reports of any serious side-effects. Some participants report a transient mild tingling, burning, or itching underneath the electrodes and headache, but no other side effects have been noted. Importantly, it remains unclear if these mild side-effects were caused by the transcranial brain stimulation. In order to monitor these side-effects, we will be administering an adverse effects stimulation questionnaire after each stimulation session to determine whether these effects were experienced. Research personnel present during these sessions will also check in with the participant periodically during the stimulation to see whether they are comfortable. If any side-effect occurs (rated by the participant as stronger than “moderate”) or the participant is experiencing severe discomfort, the stimulation will be immediately stopped.

8.3 REFERRALS FOR MEDICAL FOLLOW-UP OR PSYCHOLOGICAL COUNSELING

There is a purely theoretical likelihood that stimulation of neuronal circuits can lead to epileptic discharge. To minimize this occurrence, we screen and exclude patients with personal and family history of neurological conditions from the study. If abnormalities or a seizure is witnessed during the course of the study, a referral will be made to the UNC Department of Neurology for follow-up. In the theoretical event that a seizure is witnessed

that involves the loss of consciousness, the patient will be told not to operate a motor vehicle until cleared by the DMV.

To ensure participant comfort, a study coordinator or research assistant will periodically check in with the participant about any side-effects he/she may be experiencing during each stimulation session. Following the conclusion of the stimulation session, the participant will receive an Adverse Effects Questionnaire to report on any of the side-effects he/she may have experienced. This questionnaire reports side-effects on a likert scale (1=Absent, 2=Mild, 3=Moderate, 4=Severe). If the participant reports side-effects of Moderate to Severe intensity, a study coordinator or research assistant will discuss the side-effects experienced and note this response. The PI will be contacted based on the reported intensity on the Adverse Events Questionnaire and the participant's verbal confirmation of intensity.

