Study Duration	This study will take two months to complete.
Study Center(s)	This is a single-site study performed at the University of North Carolina at Chapel Hill.
Objectives (Purpose)	The primary objective of this study is to explore the effects of alpha oscillations on the relationship between the immune system and stress response.
Number of Subjects	20
Diagnosis and Main Inclusion Criteria	Eligible participants will be healthy adults between the ages of 18-35 with no history of autoimmune disease or mental or psychiatric disorder.
Description of Intervention (Procedures/methods)	The participants will be randomized into one of two arms: either 40 minutes of sham tACS or 40 minutes of 10 Hz tACS while in a relaxed, yet experimentally controlled state, by watching a nature movie such as "Reefscape" during stimulation.
Related IRB Applications	N/A

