3.2 EXCLUSION CRITERIA

A potential participant who meets any of the following criteria will be excluded from participation in the study:

- Diagnosis of eating disorder (current or within the past 6 months)
- Diagnosis of OCD (lifetime)
- ADHD (currently under treatment)
- Neurological disorders and conditions, including, but not limited to:
 - History of epilepsy
 - Seizures (except childhood febrile seizures and ECT-induced seizures)
 - Dementia
 - History of stroke
 - Parkinson's disease
 - Multiple sclerosis
 - Cerebral aneurysm
 - Brain tumors
- Medical or neurological illness or treatment for a medical disorder that could interfere with study participation (e.g., unstable cardiac disease, HIV/AIDS, malignancy, liver or renal impairment)
- Prior brain surgery
- Any brain devices/implants, including cochlear implants and aneurysm clips
- Traumatic brain injury
- (For females) Pregnancy or breast feeding
- Personal or family history of mental/psychiatric disorder (e.g., anxiety, major depressive disorder, schizophrenia, etc.)
- Diagnosis of an autoimmune disorder
- Failure to pass a urinary drug test at the first session.
- Anything that, in the opinion of the investigator, would place the participant at increased risk or preclude the participant's full compliance with or completion of the study

Justifications for any exclusions based on race, gender, or ethnicity: Non-English speaking individuals are excluded because the ability to accurately and completely communicate study information, answer questions about the study, and obtain consent are necessary.

Justification for excluding women or women who become pregnant: Pregnant participants will be excluded despite the fact that theoretical risk to mother or fetus is exceedingly small, since no safety data for pregnancy is known to exist for tDCS/tACS studies. We will verify pregnancy status via a urine pregnancy test for all female participants prior to receiving treatment on Day 1 of Stimulation.

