5.1 SCREENING

The screening process will involve a telephone call with the potential participant to inform of expectations and determine eligibility. A researcher will conduct a screening with each participant prior to scheduling the first session. If a participant is determined to be ineligible, data from the screening will be retained.

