9.4 TERMINATION OF STUDY

If a seizure occurs at the time of a study visit, a temporary hold will be placed over the study and further investigation will ensue. This could lead to stopping the study prematurely or continuing on with further safety measures in place. If two seizures are witnessed during the study visits, the entire study will be stopped prematurely. These individuals would be referred for further medical attention. It is very unlikely that a seizure will occur, given that previous studies using tDCS in patients with depression and schizophrenia have had no seizures occur (Berlim et al., 2013, Brunelin et al., 2012).

The study will also be stopped (at least temporarily) if studies provide evidence that transcranial current stimulation caused brain damage or other harmful effects on subjects, either short-term or long-term. Examples of findings that might trigger a safety review are the number of SAEs overall, the number of occurrences of a particular type of SAE, severe AEs/reactions, or increased frequency of events.

The reasons for stopping the study and asking for further investigation include:

- If a seizure occurs during a study visit, a temporary hold will be placed on the clinical trial

The IRB will also be informed promptly and provided the reason(s) for the termination of suspension of by the investigator, as specified by the applicable regulatory requirement(s).

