APPENDIX A: SCHEDULE OF EVENTS

	Phone Screening	Day 1 of Stimulation	Day 2 of Stimulation
Procedures			
Provide Verbal Consent	x		
Signed Consent Form		x	
Assessment of Eligibility Criteria	x	x	
Urine Pregnancy Test		x	
Urine Drug Test		x	
Baseline Assessments (PSS, CD-RISQ, PSQI)		x	
Saliva Sample		x	x
Stimulation		x	x
Stimulation Questionnaire		x	x
Saliva Sample		x	x
Final Questionnaires (PANAS, STAI)		x	x

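### Section 8.3 claims an exclusion for family history of neurological conditions that the section 3.2 eligibility list does not contain

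*Combined protocol and SAP*

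**What the plan says.** Section 8.3 raises a theoretical possibility that stimulation could provoke epileptic discharge. As the measure against it, the section states: "we screen and exclude patients with personal and family history of neurological conditions from the study".

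Section 3.2 sets the exclusion criteria. The neurological entry opens "Neurological disorders and conditions, including, but not limited to" and then lists conditions such as epilepsy, seizures, stroke and brain tumours. The seizure entry carries two exceptions: childhood febrile seizures and seizures induced by ECT. The one entry that mentions relatives reads "Personal or family history of mental/psychiatric disorder". The last entry excludes on the ground of "Anything that, in the opinion of the investigator, would place the participant at increased risk", or of doubt about compliance or completion.

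On screening, section 5.1 says "A researcher will conduct a screening with each participant prior to scheduling the first session". Section 6.1 says the telephone call collects demographics, including medical and medication history. Appendix A marks "Assessment of Eligibility Criteria" at the phone screening and again on Day 1.

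**The concern.** A risk section should describe safeguards that the eligibility list enforces. Here section 8.3 reports a family-history exclusion as something the study does, and section 3.2 does not contain it. An ethics reviewer who reads section 8.3 would take the safeguard to be in place. A coordinator who works down section 3.2 would find no line telling them to apply it.

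The event being guarded against matters to the study's continuation. Under section 9.4 one seizure at a visit puts the study on hold, and "If two seizures are witnessed during the study visits, the entire study will be stopped prematurely".

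The mismatch also leaves two procedural questions open. Section 9.3.1 discontinues participants who turn out to meet an exclusion criterion, and section 12.6 requires deviations to be logged. If a family history of epilepsy comes to light after enrolment, the protocol does not make clear whether either provision applies.

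**Working it through.** No arithmetic applies and the plan gives no figure to reproduce. The check is to take one candidate, healthy but with a first-degree relative who has epilepsy, through each place that could decide eligibility.

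1. **Section 8.3.** The candidate has a family history of a neurological condition and is excluded.
2. **Section 3.2, neurological list.** The entries are the participant's own disorders. The open-ended lead-in, "Neurological disorders and conditions, including, but not limited to", admits further disorders; it does not extend the list to relatives. Not excluded.
3. **Section 3.2, general medical or neurological illness.** This covers the participant's own illness or treatment. Not excluded.
4. **Section 3.2, family item.** It is confined to mental or psychiatric disorder. It also shows that the authors name family history when they mean it, so it should not be read into the neurological entry. Not excluded.
5. **Section 3.2, investigator's opinion.** The candidate may be excluded but need not be. Section 12.4 gives eligibility review to the study coordinator and research assistants, so without a listed criterion nothing prompts them to raise the matter.
6. **Study Summary.** Eligible participants are healthy adults with "no history of autoimmune disease or mental or psychiatric disorder". Not excluded.
7. **Section 3.1.** The inclusion criteria say nothing about family history. Not excluded.
8. **Sections 5.1 and 6.1 and Appendix A.** Eligibility is checked twice, but none of these mentions family history.

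Section 8.3 excludes this candidate; every other place either admits the candidate or leaves the decision to judgement.

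The same comparison for personal history shows a second, smaller difference. Section 8.3 excludes personal neurological history without exception. Section 3.2 covers most of it but lets through someone whose only seizures were childhood febrile or ECT-induced.

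**The case against.** The strongest reply is that section 8.3 is itself protocol text, so the exclusion is stated, and that the investigator-opinion item can carry it out. The first half stands to this extent: one cannot say the protocol lacks the rule altogether, only that two of its sections disagree. A reader might go further and infer that the sponsor meant to leave family neurological history to the investigator's discretion. The protocol does not say so; that item is simply the only listed route by which such a person could be excluded.

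A second reply is that staff may ask the question anyway. The telephone script is not in the supplied text. Nor is the approved IRB application, which section 9.1 says is followed at all times. Actual practice is therefore unknown. A question in the script would still not create a criterion in section 3.2 to act on.

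A third reply is that little follows from the gap. The protocol treats the seizure risk as theoretical only, and nothing in the documents shows that a relative's history raises it. This stands, and it limits the weight of the point. Nor is a seizure the only event that can halt the study: section 9.4 also provides for stopping on outside evidence of harm, and section 10.2.2 pauses recruitment and procedures after an unexpected event.

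**Conclusion.** The mismatch is real and rests on the text alone. Section 8.3 describes a seizure safeguard, the family-history exclusion, that the eligibility list does not contain. Staff applying section 3.2 could enrol someone section 8.3 says is excluded. The difference over febrile and ECT-induced seizures is a lesser inconsistency of the same kind.

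No probability should be attached. A reader might take a population rate of epilepsy in first-degree relatives and compute the chance that at least one of the 20 participants is affected. The documents supply no such rate. The result would also understate the number covered, because section 8.3 refers to neurological conditions generally, so a relative's stroke or dementia counts too. It would in any case be a chance of enrolment, not of a seizure or harm.

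A reader might also infer that participants are endangered or the results biased. The documents show neither. This is a point for the sponsor to consider: easily settled, and with no demonstrated effect on the trial's results.

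**What to change.** If the safeguard is intended:

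- Add a family-history item to the neurological list in section 3.2. At minimum it should cover epilepsy or seizures in a first-degree relative, since that is the part serving section 8.3's stated purpose. Whether to go wider, to the full breadth of section 8.3's wording, is the sponsor's choice.
- Ask the question at the phone screening and Day 1 eligibility checks already in Appendix A.
- Reword section 8.3 to match section 3.2, including the febrile and ECT-induced seizure exceptions, and say whether those exceptions also apply to relatives.

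The cost is one criterion, one screening question, one reworded clause and a slightly smaller recruitment pool. Section 3.3.1 counts about 30,000 potential candidates for 20 places (30,000 / 20 = 1,500 per place, before any eligibility criteria), so the loss should be easy to absorb.

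If the safeguard is not intended, remove the reference to family from section 8.3 and still align the seizure exceptions. That costs only an edit, but it withdraws the protection and does not supply it.
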